Number of pregnancies conceived in the optimal intervention time window, i.e. between start of month 4 till the end of month 6. Overall pregnancy rate. Time to pregnancy defined as both the time between a) randomization and reaching ongoing pregnancy, and as b) start of fertility treatment during the study (EM, IUI, IVF/ICSI) and reaching ongoing pregnancy. Change in semen parameters leading to different fertility treatment categorisation (for more details see page 26) between baseline and 3 months intervention, based on pre-wash total motile sperm count (TMSC) from the subpopulation from Radboudumc and sites that deliver a pre-wash TMSC before IUI/IVF/ICSI. Improvement between Impryl® and control group in fertilization rate and embryo-utilization rate in IVF/ICSI group. Fertilization rate is defined as the percentage of oocytes with 0 PN or ≥ 2 PN after insemination (IVF) or injection (ICSI). Abnormal fertilization such as 3PN will be recorded, in case this percentage differs or increases in the study group. The embryo-utilization rate (EUR) is defined as the number of high quality embryos obtained, embryo's used at transfer plus the number of embryos frozen, divided by the number of zygotes obtained in a cycle. Due to the differences in embryo evaluation and embryo selection criteria for cryopreservation, we decided to measure the relative increase in fertilization and utilization rate observed for each clinic.. Number of miscarriages defined as a non-vital intra-uterine pregnancy before 16 weeks of gestation. Live birth rate defined as beyond 24 weeks of gestation, the birth of a living child. Live births (beyond 24 weeks, defined as the birth of a living child) will be reported within follow-up time of 15 months. Furthermore the following adverse events will be reported: gastro-intestinal problems such as reflux, obstipation, diarrhea, nausea or vomiting, furthermore loss of appetite, headache, dizziness, pruritus or skin rash.

STUDY DESIGN

A multicentre randomised, double blind placebo controlled, clinical trial for Impryl® administration will be performed in the Department of Gynaecology and/or Reproductive Medicine in both academic and non-academic hospitals in The Netherlands.

The 16 centers participating in the study:

| Hospital | Principal investigator |
|---|--------------------------------|
| Radboudumc, Nijmegen | [name] |
| Slingeland Ziekenhuis, Doetinchem | [name] |

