2.2 Use of co-intervention

All couples will receive our standard care for infertility according to the guidelines of the Dutch Society of Obstetrics and Gynaecology. After diagnostic work up couples will either start with EM (6 months), IUI, IVF or ICSI. Participants will take study supplement for a maximum of 6 months, even if the fertility intervention (6 x IUI or 1 x IVF/ICSI cycles) is not completed. Co-treatment with other vitamins or supplements is prohibited. If vitamins or supplements are already used by men, a wash-out period of 3 months is recommended. Patients using other supplements will be excluded or reported as protocol violation. If after randomization it appears that a patient still uses other supplements (reported in the online questionnaire), they will be telephonically contacted and asked to stop use of other supplements. After this stop, there is a wash-out period of 72 days (duration of spermatogenesis). If no pregnancy occurs within this wash-out period the patient and data can still be included.

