5.1.2 Secondary study parameters/endpoints

Number of pregnancies conceived in the optimal intervention time window, i.e. between start of month 4 till the end of month 6.

Overall number of pregnancies meaning the cumulative pregnancy number up to 9 months after start of intervention

Time to pregnancy defined as

- a) the time between start randomization and reaching ongoing pregnancy (confirmed by ultrasound)
- b) the time between start of fertility treatment during the study (EM, IUI, IVF/ICSI) and reaching ongoing pregnancy

Change in semen parameters in IUI/IVF/ICSI group based on pre-wash total motile sperm count (TMSC), leading to different fertility treatment categorisation (EM, IUI, IVF, ICSI), from a subpopulation of patients: Radboudumc patients and patients from other sites having pre-wash TMSC as standard procedure when semen is used for IUI or IVF/ICSI.

Improvement between Impryl® and control group in fertilization rate and embryo-utilization rate in IVF/ICSI group. Fertilization rate is defined as the percentage of oocytes with 0 PN or ≥ 2 PN after insemination (IVF) or injection (ICSI). Abnormal fertilization such as 3PN will be recorded, in case this percentage differs or increases in the study group. The embryo-utilization rate (EUR) is defined as the number of high quality embryos obtained, embryo's used at transfer plus the number of embryos frozen, divided by the number of zygotes obtained in a cycle. Due to the differences in embryo evaluation and embryo selection criteria for cryopreservation, we decided to measure the relative increase in fertilization and utilization rate observed for each clinic.

Number of miscarriages (defined as non-vital intra-uterine pregnancy before 16 weeks of gestation)

Live birth rate (beyond 24 weeks, defined as the birth of a living child) within study-period of 15 months

Adverse effects

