Semen analysis will be performed two times: once during diagnostic work-up (standard care, analysis according to WHO criteria(28) and once more after approximately 3 months of using study medication (ie. after three months of IUI treatment or IVF/ICSI). At several sites, a pre-wash TMSC is standard care when performing an insemination (IUI group) and will be performed on the semen produced for IVF/ICSI as part of routine measurement before procedure. Because semen analysis performed at the time of treatment cannot be fully performed according to the WHO criteria, we will categorize the TMSC quality according to the allocated treatment category. This means, that the TMSC (evaluated at the start of treatment and after 3 months) will be analyzed according to changes in allocated treatment category based on the NVOG guideline(29). The criteria for treatment are given in the table below. A change in treatment category means an improvement in sperm quality that would allow a lower treatment category (e.g, from ICSI to IVF)

| TMSC outcome ($\times 10^6$) | WHO Diagnostic category | NVOG Treatment category |
|--------------------------------|-------------------------|---|
| > 10 | Normospermia | EM |
| 3 -10 | Mild OAT | IUI |
| 1-3 | OAT | IVF/ICSI (if after wash VCM is <0,5) |
| <1 | Extreme OAT/Azoospermia | ICSI |

OAT = oligo-astheno-teratozoospermia.

* Or IVF depending on the prediction model of Hunault and other clinical characteristics

We decided not to perform a semen analysis in the EM group due to the fact that they already have normal semen parameters at intake and the burden of an extra visit is high.

Fertilization and embryo-utilization rate

In IVF/ICSI patients fertilization rate and embryo-utilization rate are standard reported by every IVF-laboratory. Fertilization rate is the percentage of oocytes with ≥ 2 PN after insemination (IVF) or injection (ICSI). The embryo-utilization rate (EUR) is defined as the number of high quality embryos obtained, embryo's used at transfer plus the number of embryos frozen, divided by the number of zygotes obtained in a cycle. Due to the differences in embryo evaluation and embryo selection criteria for cryopreservation, we decided to measure the relative increase in fertilization and utilization rate observed for each clinic.

Transvaginal ultrasonography

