7. STATISTICAL ANALYSIS

All data will be analyzed on an intention-to-treat basis. Data of patients who are lost to follow-up, will be included in their randomised group

will be included in their randomized group:

- Patients who are lost to follow-up during the treatment period are considered not to have achieved a pregnancy.
- Patients, who are lost to follow-up right after achieving a pregnancy of less than 8 weeks of gestation, are considered not to have achieved an ongoing pregnancy
- Patients, who are lost to follow-up right after achieving a pregnancy of 8 or more weeks of gestation, are considered to have achieved an ongoing pregnancy.

In addition, a per-protocol analysis will be performed for the primary outcome and the secondary outcomes overall pregnancy number, time to pregnancy, number of miscarriages and live birth rate.

Descriptive statistics will be calculated to check for major dissimilarities between study groups with respect to baseline information. Baseline data will be described quantitatively. For continuous variables, we will examine the distribution of the observations, and if normally distributed we will summarise them as means with standard deviations (SDs). If they are not normally distributed, then medians and inter-quartile ranges (IQRs) will be reported. For dichotomous data, we will provide counts and proportions.

The primary outcome variable 'ongoing pregnancy' will be assessed as follows. The ongoing pregnancy percentages as observed in the trial will be presented for both treatment arms, overall, and separately for the three strata (i.e. EM, IUI, IVF/ICSI). In order to adjust for possible imbalances between the treatment groups, the pregnancy percentages and differences in pregnancy percentages between the experimental and control group, and the corresponding 95% confidence intervals will be estimated using a fixed effects binomial model with an identity link, including intervention, fertility treatment, centre and female age (centered). If this model does not converge, a logit link will be used.

Time to ongoing pregnancy will be evaluated by the Kaplan-Meier approach; differences between the two arms will be tested with the log-rank test. Similar analyses will be conducted per stratum (EM, IUI or IVF/ICSI). The other secondary outcomes (overall pregnancy number, number of miscarriages, live birth rate, fertilization rate, embryo-utilization rate) will be evaluated similarly to the primary outcome. Changes in semen

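### Fertilization and embryo-utilization rates are sent to a binomial model meant for one yes/no per couple; applied as written, it gives confidence intervals that are too wide or, with within-couple correlation, too narrow

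*Combined protocol and SAP*

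**What the plan says.** Section 7 gives one inferential model for ongoing pregnancy, a "fixed effects binomial model with an identity link", with intervention, fertility treatment, centre and centred female age as terms and a logit link if it does not converge. It then says of the remaining secondary outcomes: "fertilization rate, embryo-utilization rate) will be evaluated similarly to the primary outcome".

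The rates themselves are ratios within a couple. In section 5.3, "Fertilization rate is the percentage of oocytes with" a given pronuclear count. In section 5.1.2 the embryo-utilization rate is a number of embryos "divided by the number of zygotes obtained in a cycle". Section 5.2 randomises the participant, that is, the man.

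Some text points towards one rate per cycle or couple: the zygote denominator is per cycle, section 2.2 speaks of "6 x IUI or 1 x IVF/ICSI cycles", and section 5.3 says that "fertilization rate and embryo-utilization rate are standard reported by every IVF-laboratory". Section 7 does not take this up. Sections 5.1.2 and 5.3 and the Objectives also announce a different measure: "we decided to measure the relative increase in fertilization and utilization rate observed for each clinic".

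**The concern.** A binomial model fixes the variance from the mean. That is right for one 0/1 result per randomised couple. It is not right for a fraction of several oocytes, nor for oocytes that share a couple. No section supplies what would correct it: a couple effect, a dispersion parameter or a robust variance. The logit fallback keeps the same variance function, so it does not help.

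Two literal readings are open:

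- **(a)** Each couple's fraction is entered as one Bernoulli trial. The standard error is too large, and a real laboratory effect can be missed.
- **(b)** Oocytes or zygotes are the trials. With positive within-couple correlation the standard error is too small, and chance differences are reported as effects too often.

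There is also a mismatch of measure. The identity link gives an adjusted absolute difference, while the endpoint sections promise a relative increase for each clinic.

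**Working it through.** **Inputs from the documents.** Section 1.3: 600 men per arm, 1200 in total; strata EM 1 : IUI 3 : IVF/ICSI 2; two-sided alpha 5%. Section 5.2: 1:1 allocation. The IVF/ICSI stratum is therefore 1200 × 2/6 = 400 couples, 200 per arm.

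**Assumed inputs (not in the documents).** Mean rate p = 0.6; units (oocytes or zygotes) per couple m, mean 4 to 12; within-couple correlation ρ = 0.05 to 0.30; 400 couples, or 240 if only 60% are evaluable.

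**Step 1. The plan's own figure.** The plan states none for these rates. Its primary power reproduces. The pooled rate is (0.20 + 0.265)/2 = 0.2325. The null SE is √(2 × 0.2325 × 0.7675/600) = 0.02439 and the alternative SE is √((0.16 + 0.194775)/600) = 0.02432. Power is Φ((0.065 − 1.96 × 0.02439)/0.02432) = Φ(0.707) = 76.0%. Nothing below changes this.

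**Step 2. Algebra.** For a couple with m units, let D = 1 + (m − 1)ρ. The true variance of its fraction is p(1 − p)D/m.

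- Reading (a) uses p(1 − p), so model SE / true SE = √(m/D). The direction does not depend on ρ: a fraction in [0,1] with mean p has variance at most p(1 − p), with equality only if every fraction is 0 or 1.
- Reading (b) uses p(1 − p)/m, so model SE / true SE = 1/√D, which is below 1 when ρ > 0 and m > 1.
- Coverage of a nominal 95% interval = 2Φ(1.96 × ratio) − 1.

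Example, m = 8 and ρ = 0.2: D = 1 + 7 × 0.2 = 2.4. Reading (a): √(8/2.4) = 1.83, coverage 99.97%. Reading (b): 1/√2.4 = 0.65, coverage 79.4%.

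| m | ρ | (a) SE ratio | (a) coverage | (b) SE ratio | (b) coverage |
|---|---|---|---|---|---|
| 4 | 0.05 | 1.87 | 99.97% | 0.93 | 93.2% |
| 4 | 0.30 | 1.45 | 99.6% | 0.73 | 84.5% |
| 8 | 0.05 | 2.43 | 100% | 0.86 | 90.8% |
| 8 | 0.30 | 1.61 | 99.8% | 0.57 | 73.4% |
| 12 | 0.05 | 2.78 | 100% | 0.80 | 88.5% |
| 12 | 0.30 | 1.67 | 99.9% | 0.48 | 65.5% |

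**Step 3. Simulation with varying m.** Beta-binomial data, p = 0.6, Poisson numbers of units, couples with no units dropped, 400 couples, 4000 runs per cell. Type I error of the count analysis with no couple term, nominal 5%:

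| mean m | ρ = 0.05 | 0.10 | 0.20 | 0.30 |
|---|---|---|---|---|
| 4 | 7.0% | 10.1% | 14.0% | 18.2% |
| 7 | 9.0% | 12.9% | 20.6% | 28.0% |
| 9 | 11.6% | 15.7% | 23.5% | 32.2% |
| 12 | 11.8% | 19.1% | 29.0% | 36.2% |

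With 240 couples the range is 7.8% to 18.5% at mean 4 and 11.9% to 36.6% at mean 12. Reading (a) gives a reported SE 1.37 to 2.70 times the true one and type I error of 0.0% to 0.7%. Per-couple percentages with empirical variance give 4.4% to 5.6%.

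**Step 4. The planned model itself.** Identity-link binomial fits with arm, centre and female age; 400 couples, mean 8 units, rate 0.65, 1000 runs per scenario.

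- Reading (a): coverage 99.8% to 100%.
- Reading (b): coverage 95.6%, 82.9%, 76.2% and 68.5% at ρ = 0, 0.1, 0.2 and 0.3.
- Case resembling utilization (mean 5 zygotes, rate 0.45, ρ = 0.05 to 0.2): (a) 99.3% to 100%; (b) 91% down to 80%.
- Mean interval width at rate 0.65, ρ = 0.2: 0.187 under (a), 0.066 under (b), about 0.11 with a valid variance.

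**Step 5. Power for an assumed 0.60 versus 0.68.** With 400 couples: 23% to 34% under (a), against 63% to 99% for one percentage per couple in a linear model. With 240 couples: 4% to 18% against 42% to 94%.

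**Step 6. The proposed analysis.** A linear model on couple percentages with robust (HC2) variance, adjusted for 8 assumed centres and female age, has type I error of 3.9% to 5.7%. If half the couples contribute two cycles entered as separate rows, the error is 6.3% to 11.9% without clustering on couple and 4.5% to 6.5% with it.

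**The case against.** The strongest reply is that *similarly* does not mean *identically*. The primary model has a fertility-treatment term, which is constant within the IVF/ICSI stratum unless redefined, so some adaptation is unavoidable. A competent analyst might well take one percentage per couple and estimate its variance from the data, which is valid. Reading (b) also needs oocyte and zygote counts, which the documents do not clearly say are captured. This stands in part: the plan is under-specified, not certain to go wrong. But a valid reading is available only by leaving the one inferential model that section 7 names, and the hints at one rate per couple lead straight to reading (a) if that model is kept.

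The sizes rest on assumed inputs, and the 8-point effect is close to where the loss of power is greatest. Under the same assumptions with 400 couples, a 12-point difference gives 77% to 95% power under (a) against 93% to 100%. At 4 points even the valid analysis has only 21% to 60%. At mean 4 and ρ = 0.05, reading (b) costs only 2 to 3 points of coverage. All of this is true and limits the size. It does not change the direction.

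Finally, the defect is in the variance, so the binomial mean model could be kept with a robust variance at couple level: coverage is 94% to 96% for fractions and 93% to 95% for counts. That is also correct and would be an acceptable repair. A single Pearson dispersion factor on counts is less good, at about 92% for mean 8 and ρ = 0.1 to 0.3, because the number of units varies between couples.

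**Conclusion.** The concern holds. Following the model that section 7 names gives wrong confidence intervals for both rates under either literal reading. Under (a) they are too wide: SE 1.4 to 2.7 times too large and type I error below 1%. Under (b) they are too narrow: true SE 1.1 to 2.2 times the reported one, with type I error 7% to 18% at a mean of 4 units and 12% to 37% at 12. These ranges assume a rate of 0.6, ρ of 0.05 to 0.30 and 240 or 400 couples, and (b) requires positive within-couple correlation.

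The reach is limited to two secondary outcomes in about a third of the sample, with no decision rule attached. The primary result, the sample size and the 76% power are untouched. It should be settled before unblinding, because at ρ = 0.2 an analyst could otherwise choose between intervals that differ almost threefold in width (0.187/0.066 = 2.8).

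**What to change.** In section 7, take the two rates out of the list analysed like the primary outcome and state:

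1. The couple is the unit. Analyse one percentage per couple in a linear model with robust variance, adjusted for centre and female age. Section 7 already uses a linear model for the semen category change. If more than one cycle per couple contributes, cluster on couple.
2. Report by arm how many couples have no oocytes or zygotes and so no defined rate.
3. Use the centre-adjusted absolute difference for the confidence interval, and report the per-clinic relative increase descriptively, so that section 7 agrees with the Objectives and sections 5.1.2 and 5.3.
4. Settle the numerators first. The Objectives and section 5.1.2 count oocytes with 0 PN or at least 2 PN as fertilized; section 5.3 counts only those with at least 2 PN. The utilization numerator can be read as counting an embryo twice. A linear model still runs if a ratio exceeds 1; a binomial model does not.
5. If oocyte and zygote counts are held, a count model with couple-clustered variance can be a sensitivity analysis. It weights couples by their number of oocytes or zygotes, so it estimates a slightly different quantity.

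The cost is two or three sentences and a little code. The main analysis needs only the rates that laboratories already report. Intervals will be 1.2 to 2.1 times as wide as under the uncorrected count model. Against a couple-clustered count model, the SE of the per-couple analysis is 0.97 to 1.11 times as large in the scenarios of step 3. The loss grows as correlation falls: in the step 4 fits the ratio of interval widths is 0.113/0.101 = 1.12 (rate 0.45, mean 5, ρ = 0.05) and 0.081/0.067 = 1.21 (rate 0.65, mean 8, ρ = 0).

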analysis, leading to different fertility treatment categorisation, will be first calculated with descriptive statistics, with the following codes:

- 0: if there is no change in treatment category
- 1: if there is 1 category change (i.e. from IUI to EM), or -1 if it goes from less severe to severe (i.e. IUI to IVF)
- 2: if there are 2 category changes (i.e. from IVF to EM)

The changes will be summarized with descriptive statistics (mean, SD, median, range) and frequency tables per treatment and stratum. Further, the difference between the experimental and control group will be assessed with a fixed effects linear model, adjusted for centre and stratum.

Furthermore, adverse events will be summarized. Sensitivity analyses will be performed to evaluate possible effects in case of protocol amendments.

The per-protocol population will consist of all randomised patients without any major deviation from the protocol. A major protocol deviation is defined as

- Use of other nutritional supplements without a wash-out period
- Intake of study medication of less than 75% of the prescribed amount

Participants will be asked by automatic email to report in Castor their actual compliance to the intervention by taking note of total amount of consumed study medication (used boxes and tablets). Patients will also be asked to report about major changes of their lifestyle occurring during the study period (see page 22).

The results will be extracted from Castor. If there are missing data this will be mentioned along with the reason.

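### The semen category-change score has no clear code for two-step worsening and none for three-step changes, and the sections that define it conflict

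*Combined protocol and SAP*

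**What the plan says.** Section 5.1.2 defines a secondary endpoint as change in pre-wash total motile sperm count (TMSC) "leading to different fertility treatment categorisation (EM, IUI, IVF, ICSI"), measured in a subset of the IUI and IVF/ICSI couples. That is four ordered categories.

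Section 5.3 (Semen analysis) gives a table with TMSC cut points at 10, 3 and 1 million. The 1–3 million row reads "IVF/ICSI (if after wash VCM is <0,5"), and the lowest row is "Extreme OAT/Azoospermia | ICSI". The text says "we will categorize the TMSC quality according to the allocated treatment category", and then "A change in treatment category means an improvement in sperm quality that would allow a lower treatment category". The reason given for categorising is that semen analysis on a treatment day cannot fully follow WHO criteria.

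Section 7 sets the codes. The first is "0: if there is no change in treatment category". One step is 1, "or -1 if it goes from less severe to severe (i.e. IUI to IVF"). The last is "2: if there are 2 category changes (i.e. from IVF to EM"). The codes are summarised by mean, SD, median, range and frequency, and the arms are compared with a linear model adjusted for centre and stratum. No baseline semen term and no analysis of TMSC as a number are planned.

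**The concern.** A score that enters a linear model needs one value for every possible change. This list gives a sign for worsening at one step only. Whoever programmes it must decide whether a man who worsens by two steps counts as +2, is dropped, or gets a code made up at the time. The documents do not decide this, and the choice moves the result.

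The score is also coarse. A rise from 3.1 to 9.9 million scores 0, and a rise from 9.9 to 10.1 million scores 1. It is the only planned direct measure of sperm quality, which is the mechanism behind the trial's rationale, so a distorted or weak result here would be read as evidence about that mechanism.

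**Working it through.** **1. Completeness of the codes.** Rank EM = 1, IUI = 2, IVF = 3, ICSI = 4, and let score = baseline rank − 3-month rank. Section 7's own examples fit this: IUI to EM is 2 − 1 = +1, IUI to IVF is 2 − 3 = −1, IVF to EM is 3 − 1 = +2. By the same rule:

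- IUI to ICSI, or EM to IVF, is −2: not listed.
- ICSI to EM is +3 and EM to ICSI is −3: not listed.

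**2. Conflicts between sections.** Section 5.3 treats a change as an improvement; section 7 scores one-step worsening as −1. Both cannot govern. Section 5.1.2 rests the endpoint on pre-wash TMSC; in the 1–3 million row of section 5.3, IVF versus ICSI turns on an after-wash VCM. Two programmers could derive different scores from the same data.

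**3. Size of the distortion.** The plan states no figure for this score. (Its 76% power for the primary outcome reproduces at 0.760, but has no bearing here.) The documents give no TMSC distribution, so these inputs are assumptions: log-normal TMSC, treatment effect +0.15 log10 (10^0.15 ≈ 1.4-fold), between-man SD 0.55 log10, within-man SD 0.2 or 0.3 log10, median 5, 10 or 20 million, bands cut at 1, 3 and 10 million, 400,000 simulated men per arm.

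Shrinkage = 1 − literal difference / signed difference. Efficiency = squared standardised effect of the signed band score (adjusted for baseline band) divided by that of log TMSC (adjusted for baseline).

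| Median (million) | Within-man SD | Signed difference | Literal difference | Shrinkage | Efficiency of signed score |
|---|---|---|---|---|---|
| 5 | 0.2 | 0.227 | 0.212 | 6.6% | 0.53 |
| 5 | 0.3 | 0.220 | 0.160 | 27.3% | 0.66 |
| 10 | 0.2 | 0.181 | 0.169 | 6.6% | 0.43 |
| 10 | 0.3 | 0.178 | 0.130 | 27.0% | 0.55 |
| 20 | 0.2 | 0.122 | 0.115 | 5.7% | 0.30 |
| 20 | 0.3 | 0.124 | 0.093 | 25.0% | 0.41 |

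This run gives about 6–27%; a repeat gave about 7–29%. If code 2 means improvement only and uncoded men are dropped, shrinkage is about 3–15%. Two-step worsening occurred in 0.2–2.7% of placebo men and three-step changes in at most 0.23% of men. The literal code without baseline adjustment kept about 17–39% of the information (centre and stratum not modelled).

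**4. A second set of assumptions.** Median 3–40 million, SD of natural-log TMSC 0.8–1.6 between and 0.5–1.1 within men, 1.3-fold effect in the main case. Efficiency against baseline-adjusted log TMSC was 0.05–0.44 for the literal code and 0.14–0.60 for the signed score. In a mid case (median 10 million, SDs 1.2 and 0.8) with an assumed 250 men per arm, power was 0.23 literal, 0.50 signed and 0.81 for log TMSC. Three-step changes reached at most about 2.6% of men.

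**5. Direction.** Under a uniform proportional shift (0.7- to 2-fold) the sign never reversed. Reversal needs two-step worsening to drive the difference. If it occurs in 5% on placebo and 2% on Impryl, with all else equal:

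- literal code: 2 × (0.02 − 0.05) = −0.06, favouring placebo;
- signed code: −2 × (0.02 − 0.05) = +0.06, favouring Impryl.

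**The case against.** The natural reading of section 7 is that 2 means improvement: the sign convention stands one line above, the only example is an improvement, and section 5.3 speaks of improvement. Two-step worsening is then an omitted code. This stands, and it means a reader should not infer that the plan definitely scores marked worsening as benefit. It does not close the gap, because the men concerned still have no score.

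A reader might also infer that the score will point the wrong way. The uniform-shift simulations show attenuation only; reversal needs the special case in step 5 together with the literal reading.

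The endpoint is deliberately about treatment category, since the rationale includes less invasive and cheaper treatment, and a reason for categorising is stated. So scoring 3.1 to 9.9 million as 0 is intended, and replacing the endpoint with log TMSC is not warranted. The stated reason does not, however, rule out analysing TMSC beside the score, because the bands are cut from that same number.

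Two further inferences fail. In the simulations 54–80% of men score 0, but nearly equally in both arms, so this is not hidden benefit. And the footnote about a prediction model has no visible anchor in the table, so it cannot be tied to the 1–3 million row.

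**Conclusion.** The concern holds as an undefined and internally inconsistent scoring rule. What the text alone establishes is that the code for two-step worsening is ambiguous, three-step changes have no code, sections 5.3 and 7 disagree on what a change is, and one category boundary uses a measurement outside the stated endpoint.

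The size rests on assumption. Under the values in step 3, the arm difference shrinks by about 6–29% under the literal code and 3–15% if uncoded men are dropped. Information loss was substantial in every scenario tried, even with correct signs, but the percentages are illustrative ranges and not properties of this trial's data. The endpoint is secondary and measured in a subset of unstated size; the primary result is unaffected. It should be corrected, and before unblinding, so that the scoring cannot be chosen after results are seen.

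**What to change.** - Define the score on the four pre-wash TMSC bands of the section 5.3 table (>10, 3–10, 1–3, <1 million) as a signed integer from −3 to +3, positive for improvement. Use the pre-wash bands alone, for scoring only; this does not touch how couples are allocated to treatment.
- Reconcile sections 5.3 and 7, so that a change may go in either direction.
- Keep this score as the defined secondary endpoint, and add baseline band to its linear model alongside centre and stratum.
- Add a supportive analysis of log pre-wash TMSC at about 3 months, adjusted for baseline log TMSC, centre and stratum, with a stated rule for zero counts.

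The cost is a wording change and a little extra analysis. No new visits or samples are needed. The numeric TMSC must be captured in the database: no section says that the value itself is entered in Castor, so this needs checking.
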